- progression to dementia: MCI may evolve into more severe cognitive impairment with loss of functional independence, the hallmark of dementia. The annual progression rate from MCI to dementia is estimated at 10–15%, depending on underlying causes (notably AD and FTD) and individual risk factors.

Cognitive impairment may be restricted to a single domain (single-domain MCI) or involve multiple domains (multi-domain MCI). Patients can thus be classified into four clinical subtypes: (i) amnestic single-domain MCI (aMCI-SD), (ii) amnestic multi-domain MCI (aMCI-MD), (iii) non-amnestic single-domain MCI (naMCI-SD), and (iv) non-amnestic multi-domain MCI (naMCI-MD).

The MCI construct can further be staged clinically using the Clinical Dementia Rating (CDR) scale, a widely used instrument to assess cognitive decline and dementia severity over time. A CDR score of 0.5 is consistent with MCI, reflecting subtle cognitive changes exceeding normal aging (CDR = 0), but not yet meeting dementia criteria. Dementia is stratified according to severity and functional impairment into mild (CDR = 1), moderate (CDR = 2), severe (CDR = 3), very severe (CDR = 4), and terminal (CDR = 5).

Clinical characterization integrates laboratory and neuroimaging findings to guide clinicians in estimating risk and timing of progression. A central concept is that, by combining clinical subtypes with presumed etiologies, it may be possible to predict the specific type of dementia likely to emerge in patients with MCI. Current research is increasingly focused on genetic risk factors to identify individuals at higher risk of short-term progression.

**Parkinson's Disease (PD)** is the second most common neurodegenerative disorder in terms of prevalence and incidence. Its estimated prevalence is approximately 0.3% in the general population and 1–3% in individuals over 65 years of age.

Disease progression leads to degeneration of the nigrostriatal dopaminergic pathway, with marked loss of neurons in the substantia nigra pars compacta (SNpc) and subsequent dopamine (DA) depletion. Non-motor dysfunctions such as mild cognitive impairment (MCI), dementia, hyposmia, and gastrointestinal abnormalities frequently accompany disease progression.

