The pathological hallmarks of PD are intracellular  $\alpha$ -synuclein aggregates, referred to as Lewy bodies and Lewy neurites, which are found in multiple regions of the central nervous system, including the basal ganglia, dorsal motor nucleus of the vagus, olfactory bulb, locus caeruleus, intermediolateral nucleus of the spinal cord, celiac ganglia, and enteric nervous system. Genetic factors are estimated to account for approximately 25% of PD risk, with associated genetic variants differing in both frequency and relative risk. Familial Parkinson's disease (also referred to as Mendelian or monogenic PD) is characterized by rare but highly penetrant variants that significantly increase disease risk. Autosomal dominant forms (e.g., *SNCA*, *VPS35*) and autosomal recessive forms (*PARK2*, *PINK1*, *DJ-1*) represent approximately 5–10% of all PD cases.

Genetic classification of PD may guide therapeutic approaches and thereby improve patient prognosis and quality of life, including that of caregivers. The presence of pathogenic variants, together with clinical features such as age of onset and family history, can be used to stratify patients into homogeneous subgroups.

**Amyotrophic Lateral Sclerosis (ALS)** is a neurodegenerative disorder that typically begins with muscle weakness localized to one region, progressively spreading to other muscle groups. In some cases, dysarthria, dysphonia, and dysphagia may appear. A considerable proportion of patients also exhibit cognitive impairment, sometimes nonspecific, and in other cases presenting as frontotemporal dementia. Disease progression is generally rapid, although it shows substantial interindividual variability, suggesting a significant role of genetic background in disease course. Epidemiological studies have shown a slightly higher incidence of ALS in women, and a greater prevalence in Europe compared to Asia and the Middle East. Median survival is approximately 2–5 years from diagnosis, with respiratory failure representing the most common cause of death. ALS can be classified as familial (10% of cases) or sporadic (90% of cases). Environmental factors have also been implicated in disease onset. The genes most frequently associated with ALS include *C9orf72*, *SOD1*, *TARDBP*, *FUS*, and *TBK1*.

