#### 5. STUDY OBJECTIVES

The study aims to collect omics characterization for at least **1,000 patients** with neurodegenerative diseases, recruited from the Neurology and Geriatrics Units of IRCCS Policlinico San Martino (Genoa), Fondazione IRCCS Policlinico Cà Granda (Milan), and other units joining after ethics committee approval. Estimated recruitment: >400 dementia/cognitive impairment cases, >450 PD/parkinsonism cases, ~150 ALS/motor neuron disease cases. The primary goal is to identify, through whole-genome analysis, both rare and common monogenic and polygenic variants—single nucleotide variants (SNVs) and structural variants (CNVs, insertions, translocations, inversions, mobile element insertions [MEIs])—that may be causative or confer increased risk for neurodegenerative diseases. Integration with other omics sciences will enable correlation of these variants with gene, protein, and metabolic expression patterns, thereby defining distinct molecular trajectories underlying neurodegeneration and their impact on disease progression.

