##### Secondary Objectives

1. Identify causative or susceptibility genomic variants and provide accurate genetic counseling to patients and families.
2. Investigate associations between pathogenic variants in neurodegeneration-related genes and systemic comorbidities to inform prevention and early treatment.
3. Identify and characterize molecular markers (genes, transcripts, proteins, pathways) commonly dysregulated across different neurodegenerative diseases (e.g., cross-disorder gene overlap).
4. Identify cross-talk between known causative/susceptibility variants and additional transcripts/proteins/pathways influencing penetrance/expressivity of neurodegenerative disorders.

This study lays the foundation for defining homogeneous patient subgroups with combined clinical and genomic features, ultimately enabling personalized therapeutic strategies.

Given the sample size, disease-specific targeted studies may be conducted on selected subgroups. For example in Parkinson's disease, transcriptomic analyses will be performed in early-onset PD cases to detect expression or splicing defects in known PD genes, thereby revealing candidate genes with cryptic pathogenic variants through genome–transcriptome integration. Genetic data from PD patients will also be used to investigate associations between excess rare variants in predefined gene clusters (e.g., protein misfolding, mitochondrial dysfunction/oxidative stress, endolysosomal defects) and clinical phenotype, stratifying patients by progression rate: rapid progression (Hoehn & Yahr  $\geq 2.5$  at 5 years) versus slow progression (Hoehn & Yahr  $\leq 1$  at 5 years).

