#### Clinical data collection

Following consent, clinical data will be collected at participating Units and managed through REDCap. Case report forms (CRFs) will specify disease-specific data. At Visit 1, the following will be recorded:

- Sex
- Age
- Medical history
- Neurological examination
- Neuropsychological profile
- Neuroimaging findings
- Previous treatments
- Planned treatments

#### - Visit 2

If consent is given, patients/legal representatives will be informed of clinically relevant genetic variants identified. Variants associated with risk of developing other conditions (subject to confirmatory testing) will be disclosed during genetic counseling with psychological support. Patients will also decide whether information should be extended to relatives.

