## 7.4 Statistical Analysis

### Sample Size

Given the nature of this study, sample size is not determined by a formal statistical power calculation but rather by projections of i) the number of patients with neurodegenerative diseases expected to be referred to the two experimental centers during the 10-year project period, and ii) an estimated compliance rate of approximately 80%.

We anticipate enrolling at least 1,000 patients with neurodegenerative diseases, distributed approximately as follows:

- a) Parkinson's disease (PD): ~30% of cases
- b) Parkinsonism: ~5% of cases
- c) Dementias:
  - Alzheimer's disease (AD): ~30% of cases
  - Frontotemporal dementia (FTD): ~10% of cases
  - Young Onset Dementia (YOD): ~5% of cases
  - Mild Cognitive Impairment (MCI): ~5% of cases
- d) Amyotrophic lateral sclerosis (ALS): ~15% of cases.

Additionally, ~200 geriatric controls with negative neurological evaluation and negative family history of neurodegeneration will be enrolled as internal controls.

The projected cohort of ~1,000 patients is based on the epidemiology of neurodegenerative diseases observed at IRCCS Policlinico San Martino (Genoa) and Fondazione IRCCS Policlinico Ca' Granda (Milan). The expected distribution across disease categories should allow reliable characterization of clinical and molecular subgroups.

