### Statistical Approaches

Descriptive statistics will be generated to report the percentage of variants relative to the total enrolled cohort and to the control populations (European and Italian), stratified by disease (PD, parkinsonism, AD, FTD, YOD, ALS, and MCI), individual genes, and specific mutations.

Molecular–genetic data (single variants or variant groups) and clinicopathological data (diagnosis, disease stage, prognostic/predictive parameters, survival) will be analyzed using both numerical and graphical approaches. Frequency and contingency tables will be constructed, and statistical indices (means, percentiles, standard deviation) will be computed. Data will be visualized through histograms, boxplots, and scatterplots. Appropriate statistical tests—including t-tests, Fisher's exact test, and others depending on the formulated hypotheses—will be applied. Enrolled patients will be monitored through active follow-up as part of routine diagnostic care. Data regarding disability progression, disease course, and overall survival will be analyzed by diagnosis, mutation, or mutation combinations, as well as treatment received, using Kaplan–Meier survival analysis.

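### Section 7.4 assigns disability progression to Kaplan–Meier along with overall survival; with deaths censored, the curves overstate the share of patients who progress, most of all in ALS

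*Protocol*

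**What the plan says.** The last sentence of Statistical Approaches in section 7.4 covers three outcomes at once: "Data regarding disability progression, disease course, and overall survival will be analyzed by diagnosis, mutation, or mutation combinations", and continues "as well as treatment received, using Kaplan–Meier survival analysis". No other time-to-event method is named. Overall survival is listed beside disability progression as a separate outcome, and the sentence does not define the event as progression or death.

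On mortality, section 1.1 says of ALS: "Median survival is approximately 2–5 years from diagnosis". Section 5 expects about "150 ALS/motor neuron disease cases". The Sample Size text agrees ("Amyotrophic lateral sclerosis (ALS): ~15% of cases", and 15% of 1,000 is 150).

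On treatment, the Visit 1 list under Clinical data collection includes "Previous treatments" and planned treatments. Treatment is not assigned by the study (section 3).

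**The concern.** Kaplan–Meier treats a censored patient as still at risk of the event later. A patient who has died cannot progress. If deaths before progression are censored, the curve describes progression in a setting where nobody dies, not the proportion of enrolled patients who progress.

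The error rises with mortality, so it does not cancel when curves are set side by side by diagnosis, or by mutation where carriers and non-carriers die at different rates. Impact on disease progression is part of primary objective 5, and these are the only progression curves the protocol plans. A reader taking a 5-year progression risk for ALS from such a curve would take too high a figure, and a real difference between groups in the share who progress could be hidden.

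A second, conditional issue is the grouping by treatment received. If it means treatment started at any time in follow-up, a patient must survive long enough to be counted as treated, which favours treatment. If it means what is recorded at Visit 1, that bias does not arise.

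**Working it through.** The protocol gives no progression rate, event count or power for this analysis, so there is no figure to reproduce. The check therefore establishes the direction and then a range for the size.

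**Direction.** Let H1 and H2 be the cumulative hazards of progression and of death before progression. With deaths censored, Kaplan–Meier estimates 1 − exp(−H1). The proportion who progress is the integral of exp(−(H1 + H2)) dH1, which can never be larger, because exp(−(H1 + H2)) ≤ exp(−H1). This does not depend on the values chosen.

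**Size: formulas.** With constant progression hazard h and pre-progression death hazard d, at 5 years:
- 1−KM = 1 − exp(−5h)
- true cumulative incidence = h/(h+d) × [1 − exp(−5(h+d))]
- deaths before progression = d/(h+d) × [1 − exp(−5(h+d))]

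**Inputs.** Median survival of 2–5 years (section 1.1) gives a death hazard of ln2/2 = 0.347 to ln2/5 = 0.139 per year. N = 150 (section 5 and Sample Size). Assumed: h = 0.2 or 0.4 per year. The 5-year horizon is borrowed from the PD rapid and slow classes under Secondary Objectives ("stratifying patients by progression rate").

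**Case A: the full ALS death hazard acts before progression, independently of it.**

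| h | median survival | 1−KM | true incidence | excess (points) | deaths first, of 150 |
|---|---|---|---|---|---|
| 0.2 | 2 y | 63.2% | 34.2% | 29 | 89 |
| 0.2 | 5 y | 63.2% | 48.2% | 15 | 50 |
| 0.4 | 2 y | 86.5% | 52.3% | 34 | 68 |
| 0.4 | 5 y | 86.5% | 69.2% | 17 | 36 |

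First row in full: 0.2/0.547 × [1 − exp(−2.733)] = 0.366 × 0.935 = 0.342.

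**Case B: death mostly follows progression.** Assume a pre-progression death hazard of only 0.02–0.10 per year, with death after progression fast enough to keep overall median survival at 2–5 years. At h = 0.4:
- d = 0.02: 0.952 × [1 − exp(−2.1)] = 83.6%; excess 3 points; deaths first 0.048 × 0.878 × 150 ≈ 6
- d = 0.10: 0.800 × [1 − exp(−2.5)] = 73.4%; excess 13 points; deaths first 0.200 × 0.918 × 150 ≈ 28

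At h = 0.2 this case cannot reach a 2-year median: with d no higher than 0.10, at least exp(−2 × 0.30) = 55% are alive and unprogressed at 2 years.

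**Lower mortality.** At h = 0.2 and assumed median survival of 10–20 years, 1−KM is again 63.2% against a true 54.9–58.9%, an excess of 4–8 points. Under Case A, two diagnoses with the same progression hazard would therefore show identical 63% curves although 34–48% progress in one and 55–59% in the other.

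**Treatment grouping.** No document figure bears on its size. In simulations of a treatment with no effect (half of patients destined for it, late starts spread over 2 years, median survival 2 years), ever-treated versus never-treated grouping gave a hazard ratio of 0.62 if nobody was treated at enrolment and 1.00 if all treated patients already were. The answer depends entirely on that unknown.

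**The case against.** **This is detail for the SAP.** Event definitions and censoring rules are commonly settled there, and Kaplan–Meier is valid for progression or death. That is fair as far as the missing definitions go, and the separate listing of overall survival does not strictly exclude a composite. But the protocol itself chooses the method for disability progression. An SAP that follows it on the ordinary reading inherits the problem.

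**The large figures assume the wrong disease process.** Section 1.1 describes ALS progression as generally rapid, with respiratory failure the commonest cause of death, which suggests that death tends to follow progression. This stands. Case A figures should not be read as the expected error, and Case B cuts the excess at 0.4 per year from 17–34 to 3–13 points. Section 1.1 survival also runs from diagnosis, not enrolment. Section 1.1 does give a rate for another condition ("The annual progression rate from MCI to dementia is estimated at 10–15" per cent), but crossing an MCI rate with ALS mortality would be a mismatch, so it is not used.

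**Mechanism questions can be answered with hazards.** This stands too. A reader might infer that every progression comparison is invalid; it is not. Comparing progression hazards with deaths censored, including by log-rank test, remains legitimate. What fails is reading curves as the share who progress. Progression scales also differ by disease, which already limits comparison between diagnoses, but that does not help mutation groups within one diagnosis.

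**The treatment bias is not established.** A reader might infer that the curves by treatment are biased as planned. The documents do not support that: the treatment items listed are those at Visit 1, and no objective estimates a treatment effect. Only the ambiguity stands.

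**Conclusion.** The point holds for the absolute progression curves. On the ordinary reading of section 7.4, they overstate the proportion who progress, most where mortality is high, so curves from groups with different mortality are not comparable as risks. Kaplan–Meier for overall survival is sound.

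The direction is certain once deaths are censored. The size in ALS at 5 years lies anywhere from about 3 to 34 points across the cases examined, depending on the assumed progression hazard and on how many deaths precede progression. All of these figures rest on constant hazards. If the event is meant to be progression or death, the problem disappears, but the protocol would have to say so.

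The treatment grouping is secondary: a clarification to make, not a demonstrated error.

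**What to change.** Amend the final sentence of Statistical Approaches in section 7.4:

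- Keep Kaplan–Meier for overall survival.
- For disability progression, use Aalen–Johansen cumulative incidence with death as a competing event, or state explicitly that the event is progression or death.
- State that treatment received is classified from what is recorded at Visit 1 and that these curves are descriptive. If treatment started later is to count, use a time-varying or landmark analysis.

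The cost is a few sentences and slightly more analysis work. The composite is simpler but answers a different question: at h = 0.2 under Case A it gives 1 − exp(−5(h+d)) = 82–94% at 5 years for median survival of 5 down to 2 years, against 48–34% who progress. Visit 1 classification uses data already planned. The time-varying or landmark option needs treatment start dates, which are not among the listed items and would have to be added to the CRF, most cheaply before follow-up accumulates.

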## 8. CLINICAL RISK

Blood samples will be collected from these patients (San Martino and Milan) or, if necessary, through an ad hoc collection (IRCCS Foundation, Milan). No additional risks are expected for enrolled patients, since the study does not foresee further procedures but is limited to the collection of clinical data.

### Screening Failure

If it is determined that a subject is not eligible for enrollment despite having provided informed consent (e.g., due to an incorrect diagnosis), the patient will be classified as a screening failure. In such cases, all collected data will be deleted and any biological samples destroyed.

### Withdrawal from the Study and Early Discontinuation

Participants are free to withdraw from the study at any time without providing any explanation.

Early withdrawal may also occur if the Sponsor decides to terminate the study prematurely, following discussion with the Ethics Committee.

The Sponsor may decide to discontinue the study early under specific circumstances, such as inadequacy of the site or investigators, financial reasons, insufficient recruitment, or intervention by the Ethics Committee.

### Management of Adverse Events

As this is not an interventional study, no adverse events are expected. Should an adverse event occur during the collection of biological samples, it will be managed according to standard clinical practice.

## 9. ETHICAL ASPECTS

The study will be conducted in accordance with the principles of the Declaration of Helsinki and with international standards of Good Clinical Practice. The protocol and the patient information/informed consent form must be approved by the Ethics Committee before enrollment of patients at the Clinical Center.

The investigator is responsible for notifying the Ethics Committee of any protocol amendments, in compliance with current regulations, and for retaining copies in their records.

Projects involving genomic studies raise several challenges related to the increasing use of data. First, technical challenges arise from the need for computational resources for big data analysis, as well as for data storage and management. The growing volume of data produced by research studies requires high-performance computational systems and large storage capacity, which often becomes a limiting factor for small to medium-sized centers.

The most critical challenges, however, are ethical in nature. The accumulation of personal information inevitably makes systems responsible for ensuring privacy vulnerable. Furthermore, the availability of a wide range of information (both clinical and genetic) increases the likelihood of incidental or unexpected findings. For this reason, the scientific community has been working for years on developing regulations for the use of such data.

An example is that of *secondary/incidental findings (SF/IF)* in genomic sequencing. The literature includes numerous publications and guidelines from Scientific Societies (e.g., the American College of Medical Genetics, the European Society of Human Genetics) that define SF/IF as “genetic variants identified through genomic sequencing that are unrelated to the investigated condition” (ACMG, 2013). These findings therefore include many genetic and genomic variants present in every individual.

For the purposes of this project, and according to the relevant literature, secondary findings are defined as “information concerning an individual’s health and/or relevant to their reproductive or existential choices, particularly genetic data emerging in the course of a biomedical research project such as the present one, but not included among its primary or secondary objectives, as a result of practices, analyses, and/or investigative methodologies commonly used in that type of study” (CNR Research Ethics and Bioethics Commission, 2023).

Among the possible secondary findings that may emerge in omics-based research projects, a list of genes has been identified that are associated with highly penetrant diseases, for which early detection is linked to reduced morbidity and mortality (*actionable genes*, ACMG 2023). This periodically updated list will serve as a reference throughout the present project.

## 10. PRIVACY AND CONFIDENTIALITY

The Sponsor, Co-Sponsor, and Investigator act as independent data controllers for the processing activities under their respective responsibility, in compliance with current data protection regulations (Regulation (EU) 2016/679, GDPR, as amended), as well as in accordance with the provisions of the Italian Data Protection Authority (“Garante”) ruling of July 2019 on the processing of special categories of data pursuant to Article 21, paragraph 1 of Legislative Decree 10 August 2018, no. 101.

Researchers and designated personnel involved in the study and authorized to process data operate in accordance with the “Regulation (EU) 2016/679 of the European Parliament and of the Council of 27 April 2016.”

In particular, each participant is informed, through an appropriate information sheet, of the purposes, conditions, and modalities of data processing. Participants will be assigned an alphanumeric identification code specific to the study, which will enable pseudonymized registration of their data. Throughout the study, participant data will be handled exclusively in association with the assigned study code, including for scientific congress presentations or publications, whether as individual cases or in aggregated form.

Similarly, codes assigned by the healthcare facility to biological samples and patients will not be shared with collaborating centers. Only the Principal Investigator, or a designated member of the study team (clinical staff directly involved), will be able to link such codes to the study ID.

For data verification purposes, authorized representatives of the Sponsor and Competent Authorities may request direct access to parts of the study documentation, including participant-related documents.

Privacy compliance is supervised by the Data Protection Officers (DPOs) of the individual project partners. Their role is to ensure the correct application of privacy regulations, confirm that information systems comply with legal requirements, conduct risk assessments, and recommend any additional technical safeguards, as well as define the data management policies to be followed by operational staff.

The Data Controllers are:

- **IRCCS Ospedale Policlinico San Martino**, [name].
- **Fondazione Istituto Italiano di Tecnologia (IIT)**, [name] ([contact]).
